## Recruitment and Retention Plan

Study participants will be individuals residing in the State of Texas. Recruitment efforts may include direct mail from registries, mailing flyers, public service announcements, media interviews, and advertisements on online social media, radio, television, and newspaper outlets (see Appendix R), and digital advertising companies. Institutional channels may be used to aid study recruitment, including, but not limited to, patient database data mining (e.g., EPIC, TRTP database) for potentially eligible patients and other internal recruitment methods (e.g., MyChart to send messages, newsletters, inside MD Anderson television channels). The Tobacco Research and Treatment Program's web screener database for tobacco users, outlined in IRB-approved PA18-0423, also may be used as a recruitment source for this study. This database houses data collected from an internet-based screening questionnaire to recruit tobacco users from the Houston area, as well as across Texas more broadly, who may be interested in participating in tobacco use and cessation studies at MD Anderson Cancer Center. PA18-0423 allows the sharing of data with IRB-approved MD Anderson protocols. We will rotate through various venues throughout the recruitment period. We have many years of experience using these venues for quitting and nonquitting tobacco clinical trials recruitment. The MD Anderson Marketing and Communications departments may also assist in arranging interviews, public service announcements, and social media communications to assist in study recruitment. Additionally, we may engage the services of external clinical trials recruitment services to obtain contact information of prospective study participants. We anticipate no difficulty in recruiting the required number of participants.

**Table 1.** Inclusion Exclusion Criteria.

**Inclusion Criteria:**

- Aged 21 years or older
- Reports being a daily or non-daily smoker (any self-reported smoking in the past 30 days)
- Have an address where he/she can receive mail
- Able to follow verbal and written instructions in English and complete all aspects of the study as determined by PI
- Willing to have urine biospecimen samples taken, either in-home and returning them by mail, or in-person at an approved collection site.
- Willing to use tobacco-flavored study electronic cigarettes
- Agrees to comply with all MD Anderson institutional policies related to COVID-19 screening prior to any in-person research visit.
- The individual agrees to not engage in study procedures or interactions with study personnel while operating a vehicle.

**Exclusion Criteria:**

- Individuals who report depressive symptoms in the moderately severe or severe range on the PHQ-9 (scores of 15 or above) or who report current suicidal ideation on the PHQ-9
- Uncontrolled or unstable medical condition (e.g., uncontrolled hypertension, angina, diabetes).
- Evidence of cognitive deficits or instability that would preclude reliable study participation.
- Being pregnant, engaging in breast-feeding, or being of childbearing potential and engaging in sexual activity that could lead to pregnancy and is not protected by a medically acceptable, effective method of birth control while enrolled in the study, as determined by self-report. Medically acceptable contraceptives include: (1) approved hormonal contraceptives (such as birth control pills, patches, implants or injections), (2) barrier methods (such as a condom or diaphragm) used with a spermicide, or (3) an intrauterine device (IUD). Contraceptive measures sold for emergency use after unprotected sex are not acceptable methods for routine use.
- Considered by the investigator to be an unsuitable or unstable candidate (including but not limited to the following situation: unwilling or unable to comply with study procedures)
- Individuals who reside in an area that is outside of our shipping company's area of operation or in a jurisdiction outside of our medical staff's licensure (if unable to attend in-person clinic visits) AND who decline or are unable to come in to clinic to provide necessary samples and/or collect study products.

or virtual visit (up to \$100) (excluding the telephone AE follow-up), up to \$40 for completing

To facilitate participant retention and compliance with study procedures, we will offer financial compensation. Enrolled participants will have the opportunity to receive a potential maximum compensation of \$522 each (see Appendix V). Participants will be compensated up to \$25 for each in-person

study questionnaires prior to visit (\$10/instance), \$2/instance for completing short message service (SMS)-prompted once daily smartphone Qualtrics assessments of product use for 42 days (up to \$84), and \$2/day for completing random smartphone EMA assessments (completed 2 times/day) for 42 days (up to \$168). Additionally, we will provide \$50 to participants at the end of both phases 2 & 3 contingent upon the return of all used and unused SREC cartridges (up to \$100 total). We have used this EMA compensation scheme successfully in other studies, obtaining over 75% response rate to individual EMA assessments. We also use automated text messaging to remind participants of appointments and provide feedback on missed EMA assessments. Also, because participants will be asked to use their personal smartphone devices and personal data plans for study related assessments, they will receive an additional \$30 at the end of study participation. Participants without a smartphone, or who would prefer not to use their own device, may be provided with a smartphone and service plan for the duration of the study. For this group, they will receive the additional \$30 for returning the smartphone at the end of study participation. Participants will not be compensated for the final safety telephone call since no research assessments will be administered. Payment for the visits will be issued either upon receipt of the samples at MD Anderson or upon shipping package tracking showing sample movement back to our clinic.

COVID-19 adaptation: No adaptations needed.

## Participants

We will recruit up to 196 participants (98 male and 98 female adult CC smokers) from the state of Texas and/or Houston metropolitan areas. Inclusion/exclusion criteria are described in **Table 1**. Note: For the purpose of eligibility requirements and ongoing smoking status, "cigarettes" will also include the tobacco product that is commonly known as "little cigars". Little cigars are machine-manufactured and sold in packs similar to cigarettes. They are often smoked by individuals of limited means because they are cheaper than conventional cigarettes.

COVID-19 adaptation: While this study is being conducted virtually, we will expand participant recruitment to the state of Texas.

## Procedures

**Phone screen: Initial eligibility.** All participants will be screened by phone (see Appendix S) by a trained study staff member to determine initial eligibility (e.g., age, interest in trying ECs). Women of child-bearing potential will be asked about pregnancy and lactation status and contraception use at phone screen. In the event a female subject becomes, or is found to be, pregnant while active in the study, the subject will be withdrawn from the protocol, referred to their primary care physician (PCP), and will be offered smoking cessation counseling at that time.

Eligible participants will be scheduled for the initial screening visit (V0), which may be done in-person or virtually through an institutionally approved platform (e.g., Zoom). All participants who are initially eligible will be informed that they may be sent an email with a questionnaire consent statement, and, should they consent, they will be automatically connected to questionnaires hosted on MD Anderson's Qualtrics platform, prior to their scheduled screening visit. Participants may receive a phone call, email, and/or text message before their laboratory or virtual sessions to remind them of the appointment. Eligibility criteria including age, CPD, stable address, interest in trying ECs, and pregnancy-related criteria will be collected through self-report during the telephone screening.

COVID-19 adaptation: As applicable during the SARS-CoV-2 pandemic and recovery phase, MD Anderson institutional screening requirements will be reviewed with the participant and their verbal acknowledgement obtained before scheduling the in-person screening visit.

**In-person or virtual screening session (V0).** The consenting staff member will review the Informed Consent Document and all relevant study information. They will then review any questions the patient may have, and confirm that they understand the nature of the research being performed. Fluency in spoken and written English will be assessed by a TRTP study staff member during the consenting process by asking the participant to read aloud a section of the Informed Consent Document. This will be noted in the Documentation of Informed Consent. Additionally, information provided at the time of the phone screen may be verified prior to consent.

Participants will be instructed to smoke *ad libitum* prior to this session. Prior to the session, the participant will be asked to complete basic demographics, smoking, tobacco product use, and health history questionnaires used in our previous studies  that will be reviewed and approved for eligibility by a licensed medical provider following the visit. CC, SREC, and other tobacco product use eligibility criteria will be evaluated using a timeline follow back procedure  and smoking history measures used in previous studies . These questionnaires may be pushed by our institutional Qualtrics server to be completed electronically (via text or email) prior to the session. Current major depressive disorder (MDD) and suicidality will be identified using the Patient Health Questionnaire (PHQ-9; see Appendix L) . The screening session and the three return visits are each expected to last approximately 3 hours. The final safety telephone call will assess any ongoing adverse effects and should last approximately 10 minutes.

**COVID-19 adaptation:** Eligible participants will be scheduled for a virtual screening session using an institutionally approved platform, such as Zoom. If we are unable to collect any required biological specimens through mail, the participant may be asked to go in-person to conduct the tests through an approved collection site. Approved sites may include University of Texas MD Anderson, University of Texas sister institutions including the Center for Neurobehavioral Research on Addiction (CNRA) at University of Texas Medical School, other universities or hospitals located in Texas, and/or contracted commercial vendors.

**Baseline Medical Clearance.** Following the completion of the baseline visit, a member of the medical team (Physician assistant and/or the Physician) will review all relevant data collected at screening and will provide their clearance for the participant to proceed to Visit 1. The study Physician will have the final review of the data and will complete the final eligibility sign off prior to randomization. In the event the Physician is not able to sign-off prior to the visit (due to being out of office), the Principal Investigator may provide the initial sign-off so that the visit may proceed, and the physician will sign-off upon their return.

Following the medical team clearance to proceed to Visit 1, a study supply kit will be sent containing the urine specimen collection supplies and other study materials.

**Study Supply Kit: Baseline Screening Visit.** The following items are included in the initial study supply kit:

- Written instructions
- Urine collection kit
- Reloadable gift card (e.g., Bank of America or another approved institutional option)
- Return address label, postage-paid, and box for shipment
- Biospecimen bag, absorbant test tube sleeves

The study specific supplies will be shipped to eligible participants and tracked through eShipGlobal or a comparable system within two business days of completion of the Baseline

Screening Visit. Mailing time may be adjusted due to carrier delays, holidays, or any other factor impacting delivery time. Written instructions will be provided and the research team will be available to guide participants through the sample collection process as needed. The participant must complete and return the required samples to the MD Anderson research team prior to Visit 1, or Visit 1 may be rescheduled.

[figure not shown]
**Phase 1: UB Baseline (weeks 1-2).** During this phase, participants will be instructed to smoke their usual brand *ad libitum*. Measures specific to this phase will be captured at a virtual or in-person visit at the end of week 2. Daily smartphone EMA assessments, as described below, will occur throughout Phase 1. Refer to **Figure 1** for a timeline of study procedures.

COVID-19 adaptation: No adaptations needed.

**Phases 2 & 3: SREC-NIC and SREC-PLA use (weeks 3-4, 5-6).** During Phases 2 & 3, participants will be provided with SREC-NIC or SREC-PLA, in a counter-balanced fashion (i.e., half will receive SREC-NIC during phase 2 and SREC-PLA during phase 3). The subjects will be randomized on a 1:1 ratio and will be assigned to their randomization group through the protocol specific TRTP database. 50% (70 subjects) will receive the Active study product first and the placebo second and 50% will receive the Placebo study product first and the active study product second. During the randomization process, participants will be stratified by gender for order of exposure to SREC-PLA and SREC-NIC. At the beginning of each phase, each participant will receive 2 SREC devices with non-removable rechargeable batteries (3.3 v, 1000 mAh battery), 1 USB recharger, a 2-week supply of sealed SREC tanks (14 pods; containing either nicotine or placebo e-liquid), a user manual, and a carrying pouch. The SRECS are produced by NJOY LLC (Glenns Ferry, ID) under NIDA contract, and are available in two nicotine doses, 5% (~59 mg/ml nicotine) and 0% (0 mg/mL nicotine; placebo), a single flavor (nicotine), and in sealed disposable pods that deliver <350 puffs/pod . Participants will be instructed to use the SREC during Phases 2 and 3 whenever they get the urge to smoke, but will not be penalized for using their UB CCs or other nicotine products (including other ECs), as product use is a dependent measure in this study. The use of UB CCs and the study products will be documented daily by the participant in Qualtrics as part of the EMA.

At the beginning Phase 2, participants will receive training in how to use the SREC product. They may be shown a brief video demonstrating its use followed by a hands-on training which will include assembly (battery and tank), turning the SREC on and off, puffing, and recharging the battery. The training session will last 30 minutes and will include a minimum of three bouts of 10 puffs each in which the user will be encouraged to vary puff topography to maximize desired sensory qualities of product use. This procedure is currently being used by us in our active EC grant (R01DA042526), and has been found to result in users achieving

**Figure 1.** Timeline of study procedures.

condition. The Program Director, who will not have participant contact, will manage the inventory and labeling of blinded products. Blinded study staff will distribute the product to patients at each visit. The study medical monitor ([name]) and collaborator on respiratory symptom assessment ([name]) will be provided unblinded information on SREC condition by the Program Director, per their request. In the case an unblinding needs to occur, the study team will notify the IND sponsor Clinical Trials Safety Team, the DSMB, and the IRB. The SRECs will be obtained through NIDA's procurement process.

Measures specific to these phases will be captured at in-person or virtual visits at the end of each phase (weeks 4 & 6). Daily smartphone EMA assessments will occur throughout all phases.

**COVID-19 adaptation:** Participants will be mailed their 2-week allotment of study ECIGs prior to the start of phases 2 and 3 by a study staff member blinded to the nicotine dose. Additionally, participants will be asked to provide the urine samples during each phase and mail those back to the primary MD Anderson site. All supplies to collect the samples, as well as shipping materials and postage will be provided. Visit payment will be issued once MD Anderson staff are able to track movement on the return package. Alternatively, participants may be asked to collect the study ECIGs and/or provide their urine samples in-person from an approved site. Approved sites may include University of Texas MD Anderson, University of Texas sister institutions including the Center for Neurobehavioral Research on Addiction (CNRA) at University of Texas Medical School, other universities or hospitals located in Texas, and/or contracted commercial vendors.

**Study Supply Kit: Treatment visits.** The following items are included in each treatment visit study kit.

- Urine collection kit
- Return address label, postage-paid, and box for shipment
- Biospecimen bag, absorbant test tube sleeves
- e-cigarette kit
- Written instructions

Treatment study kits will be mailed approximately 5-7 days prior to each treatment visit. Mailing time may be adjusted due to carrier delays, holidays, or any other factor impacting delivery time. Participants will be instructed to complete the required visit samples and place in the mail to be returned to MD Anderson.

**Adverse Event Safety Assessment.** 30 days (+/- 7 days) following the end of Phase 3, study participants will complete a telephone visit with study staff to assess ongoing adverse events.

**Post-study smoking cessation treatment.** We will offer all participants 8 weeks of free smoking cessation treatment, which may include nicotine replacement therapy (NRT; nicotine patch and lozenge) and smoking cessation counseling, at the end of their study participation. Alternatively they may be referred to another smoking cessation study. It is not the intention of this phase of study to evaluate the efficacy of EC for smoking cessation, but rather to facilitate smoking cessation by offering free treatment at the conclusion of EC exposure. This fulfills what we see as a strong ethical obligation to treat smokers that enter our research programs. NRT and counseling will be administered by MD Anderson's Tobacco Treatment Program (TTP), headed by Drs. [name] (Co-I) and [name] (Co-I), which provides free treatment to all

**Table 2.** Project measurement, by time point.

Week	-1	0	2	4	6	10
Visit	T0	0	1	2	3	T1
Telephone contact	x					x
In-person or virtual Session		x	x	x	x	
Initial baseline measures:						
Initial eligibility screen (e.g., age, nicotine product use)	x					
Demographics, smoking, tobacco product use, and health history		x				
PHQ-9	x					
Tobacco Products and Risk Perceptions Survey (TPRPS)	x					
Environmental Tobacco Smoke Exposure Questionnaire (ETSEQ)	x					
Product Use:						
Timeline Follow Back (TLFB) of CC & other product use	x	x	x	x	x	
Timeline Follow Back (TLFB) of SREC use			x	x		
Urine sample to measure nicotine, cotinine, nicotelline and anabasine		x	x	x		
Smartphone EMA of product use 	x	x	x	x		
Ongoing Adverse Event (AE) Assessment			x	x	x	
Health Changes Questionnaire		x	x	x		
Product Acceptability:						
Product Evaluation Scale (PES) - CC	x	x	x	x		
Product Evaluation Scale (PES) - SREC			x	x		
Perceived Health Risk Questionnaire (PHRQ) – CCs & ECs	x	x	x	x		
Perceived Health Risk Questionnaire (PHRQ) – SRECs			x	x		
Implicit Association Test (IAT) – CCs & ECs	x	x	x	x		
Brief Smoking Consequences Questionnaire-Adult (BSCQ-A)	x	x	x	x		
EC-specific Brief Smoking Consequences Questionnaire-Adult (EC-BSCQ-A)	x	x	x	x		
Product Reinforcement:						
Purchase task (PT) - CCs	x	x	x	x		
Purchase task (PT) - SRECs			x	x		
Respiratory Health and Symptoms						
American Thoracic Society questionnaire (ATSQ)	x	x	x	x		
Nicotine Dependence Symptoms:						
Fagerström Test for Cigarette Dependence (FTCD)	x	x	x	x		
Penn State Electronic Cigarette Dependence Index (PSECDI)			x	x		
Minnesota Nicotine Withdrawal Scale-Revised (MNWS)	x	x	x	x		
Positive and Negative Affect Scales (PANAS)	x	x	x	x		
Questionnaire of Smoking Urges-Brief (QSU-Brief)	x	x	x	x		
Smartphone EMA of nicotine dependence symptoms 	x	x	x	x		
Other:						
Assess Contraception use	x	x	x	x		
Update Menstrual Phase information	x	x	x	x		
Note.  Smartphone EMA will be assessed daily throughout the 6-week study period.						

Texas sister institutions including the Center for Neurobehavioral Research on Addiction (CNRA) at University of Texas Medical School, other universities or hospitals located in Texas, and/or contracted commercial vendors. TLFB will be collected virtually by study staff. We will also provide postage-paid shipping supplies for participants to return all used and unused e-cig pods. Questionnaires will continue to be administered electronically via the institutionally-approved web-based Qualtrics platform administered over the study smartphones.

**Demographics, smoking, tobacco product use, and health history.** As part of the screening session, and to capture information for the exploratory aim, participants will complete basic demographics, smoking, tobacco product use, and health history questionnaires used in our previous studies (see Appendices C and I). Menthol CC preference will also be captured. Recent (past 30 days) and prior EC use and EC flavor preference (if ECs have been used in the

MD Anderson patients, family members, and employees, or by the Tobacco Treatment Program Quitline, also headed by [name]. The TTP has a 9-month cessation rate of 36%-47%. An alternative options would be a referral to a cessation trial, based on availability.

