**Assessment of nicotine dependence symptoms.** As part of Aims 1 & 2, participants will complete questionnaires assessing nicotine dependence symptoms, including CC dependence (Fagerström Test for Cigarette Dependence [FTCD; formerly the FTND; see Appendix C]), EC dependence (Penn State Electronic Cigarette Dependence Index [PSECDI; see Appendix J]), nicotine withdrawal (Minnesota Nicotine Withdrawal Scale-Revised [MNWS; see Appendix H]), affect (Positive and Negative Affect Scales [PANAS; see Appendix I]), and craving to smoke (Questionnaire of Smoking Urges-Brief [QSU-Brief; see Appendix N]) at each study visit.

During all phases, SMS/Qualtrics will be used to collect 2 daily random smartphone EMA measures of nicotine dependence symptoms, including nicotine withdrawal, craving, and affect, based on 8 items from the QSU, PANAS, and MNWS. Further details about the 2 daily smartphone EMA measures, as well as the once daily assessments of product use, are described above in the "Assessment of product use" section.

**Assessment of respiratory and other symptoms.** We will also assess respiratory symptoms at each visit using the American Thoracic Society questionnaire (ATSQ). The ATSQ is an 8-item questionnaire that assesses symptoms including coughing, wheezing, phlegm production, shortness of breath. An email will be sent to project staff when a participant completes the ATSQ and has a total score of >3 on questions #4-8. Staff will assess symptoms with the participant at the next visit. If symptoms present prior to the start of study product (V0 or V1), staff will add the conditions to the medical history. If the elevated score presents while on study product, staff will assess changes in symptoms and severity and log an adverse event, if indicated.

Study Medical Monitor [name] will oversee the collection, review, and attribution of adverse events (AEs) in this study and will consult with [name] on respiratory-

related AEs, as needed. The physician may delegate to other members of the medical team the task of a preliminary review of the adverse event, attribution, and recommended action plan. The physician will then complete the final review of the adverse event, confirm attribution and sign off on the adverse events.

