#### ***Adverse Events and Serious Adverse Events***

An adverse event is the appearance or worsening of any undesirable sign, symptom, or medical condition occurring after starting the investigational component even if the event is not considered to be related to study component. Medical conditions/diseases present before starting study component are only considered adverse events if they worsen after starting study drug. Abnormal laboratory values or test results constitute adverse events only if they induce clinical signs or symptoms, are considered clinically significant, or require therapy.

The investigator (or physician designee) is responsible for verifying and providing source documentation for all adverse events and assigning the attribution for all adverse events for subjects enrolled. The physician may delegate to other members of the medical team the task of a preliminary review of the adverse event, attribution, and recommended action plan. The physician will then complete the final review of the adverse event, confirm attribution and sign off on the adverse events. Since this is an ITP study, safety will be monitored by the MD Anderson IND Office. Adverse event terminology and grades will be determined using the Common Terminology Criteria for Adverse Events (CTCAE), version 5.0, published by the U.S. Department of Health and Human Services. Adverse events will be reviewed by our medical personnel and the PI. Adverse event monitoring will continue up to 30 days after medication is completed. If an AE is spontaneously reported after the AE reporting period is over, the AE will be recorded in the patient's progress notes. Those AEs that are probably, possibly or definitely related to treatment will be followed until resolution or end of study, whichever comes first. In the case of reports of suicidal ideation, depression or anxiety which we believe may be related to treatment, if possible, we will engage in our normal psychological assessments. The Addiction Psychiatrist will determine the course of clinical management according to methods of good clinical practice. The PI or physician is responsible for determining the final attribution of adverse events to study medication.

Based on the new safety information related to vaping and e-cigarette use, this protocol will be reviewed every 6 months for safety monitoring by IRB Continuing Review and MD Anderson's Data Safety Monitoring Board (DSMB).

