### ***Specific Instructions for Adverse Events Recording***

For this project, adverse events will be recorded according to the Recommended Adverse Event Recording Guidelines for Phase III protocols (see **Table 4**). Relevant medical history and baseline symptoms will be collected at the initial screening visit (V0) and V1, and will be graded according to the CTCAE 5.0 criteria and sent to the medical team for review. Any member of the medical team may review the medical history as part of the pre-randomization review process to clear the participant to V1. The study physician will complete a final eligibility review and sign-off prior to randomization. Adverse events will be recorded starting at every contact once the participant has started study product, which will be V2 and V3. In addition, the participant will complete a 30-day Adverse Event telephone assessment (30 days after V3, with a window of +/- 7 days) to follow up on any ongoing adverse events only.

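### The medical monitor who oversees adverse event attribution can obtain the SREC condition on request, and attribution decides whether non-serious grade 2-3 events are recorded

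*Combined protocol and SAP*

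**What the plan says.** **Access to the code.** Procedures (Phases 2 & 3) keeps the staff who hand out product blinded. It then says that the medical monitor and the collaborator on respiratory symptoms "will be provided unblinded information on SREC condition by the Program Director, per their request". The next sentence adds: "In the case an unblinding needs to occur, the study team will notify the IND sponsor Clinical Trials Safety Team, the DSMB, and the IRB".

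**Who attributes.** Measures (respiratory and other symptoms) says the medical monitor "will oversee the collection, review, and attribution of adverse events (AEs) in this study" and consults on respiratory AEs as needed. The consultant's name is removed, but the role matches the respiratory collaborator. Others also have a part. Under Adverse Events and Serious Adverse Events, "The investigator (or physician designee) is responsible for verifying and providing source documentation for all adverse events and assigning the attribution for all adverse events". After a preliminary review that may be delegated, "The physician will then complete the final review of the adverse event, confirm attribution and sign off on the adverse events". The same section closes by giving final attribution to the PI or the physician.

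**What is recorded.** Specific Instructions for Adverse Events Recording states that "adverse events will be recorded according to the Recommended Adverse Event Recording Guidelines for Phase III protocols", pointing to Table 4. The AE definition itself does not depend on causality: an event counts "even if the event is not considered to be related to study component".

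**The concern.** Blinded AE assessment protects a safety comparison because the assessor's expectation cannot depend on the product. Here the monitor may know the product when causality is judged, and causality decides whether a grade 2 or 3 event enters the record. The same headache could be called possible in one phase and unlikely in the other, then kept in the first and left out of the second.

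The plan supplies expectations that could drive this. Its section on adverse experiences with electronic cigarettes lists airway irritation, cough, headache and nausea with vaping, and withdrawal effects particularly with placebo. The distortion could therefore run in either direction, depending on the symptom.

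At stake is any nicotine-versus-placebo reading of the recorded non-serious events. The team has drawn such a reading before: under Safety of EC products it compares AE proportions between phases of its current study (18.0% and 15.3%) and concludes on product safety.

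**Working it through.** The plan gives no figure for this point, so there is nothing to reproduce. The check has two steps.

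**Step 1: does attribution decide recording?** Reading the Phase III entries of Table 4:

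| Attribution | Grades recorded under Phase III |
|---|---|
| Unrelated, unlikely | 4, 5 |
| Possible, probable, definitive | 2, 3, 4, 5 |

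Grade 1 is never recorded, and grades 4-5 always are. Only at grades 2 and 3 does the result turn on attribution. Grade 2 is explicit in the table. For grade 3 and above, the cells in the lower three rows are blank in the readable text and are taken as merged with grade 2. Serious Adverse Event Reporting sends all serious events to the IND Office whatever the attribution. What remains exposed is the non-serious grade 2-3 event.

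**Step 2: how large could the effect be?** Let

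- r = true rate of non-serious grade 2-3 events, equal in both conditions;
- u = share of attributions made with the code known;
- p = probability of possible or higher when the code is known (differs by condition);
- p0 = the same probability when blinded, set at 0.5.

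Recorded rate = r × [u × p + (1 − u) × p0].

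The values of p, p0 and u are assumptions. For r, 15.3% is borrowed purely as an illustration: it is the proportion with any AE, of any grade, in the e-cigarette phases of the team's other study, with a different product. The count uses n = 140 per condition, from Power and Sample Size.

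With p = 0.60 on nicotine and 0.40 on placebo:

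| u | Nicotine | Placebo | Ratio |
|---|---|---|---|
| 1 | 0.153 × 0.600 = 9.2% | 0.153 × 0.400 = 6.1% | 1.50 |
| 0.5 | 0.153 × 0.550 = 8.4% | 0.153 × 0.450 = 6.9% | 1.22 |
| 0.25 | 0.153 × 0.525 = 8.0% | 0.153 × 0.475 = 7.3% | 1.11 |
| 0 | 0.153 × 0.500 = 7.65% | 0.153 × 0.500 = 7.65% | 1.00 |

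The first row is 12.9 versus 8.6 participants out of 140. The ratio does not depend on r, which cancels; the absolute difference does. At u = 1 the difference is r × 0.20, so 1.0 percentage point at r = 5% and 6.0 at r = 30%. A more extreme split of 0.80 versus 0.20 gives a ratio of 4.0 at u = 1 and 0.575/0.425 = 1.35 at u = 0.25.

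**The case against.** The strongest reply is that a reader might infer that the only two people who attribute AEs are both unblinded, and that the product comparison of AEs is therefore biased. The documents do not support that.

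- **Attribution is shared.** The collaborator is only consulted. The investigator or designee, the physician and the PI all have stated roles, and none of them is given code access under those titles. Whether the signing physician is the medical monitor cannot be told with names removed. If they differ, the final signatory may well be blinded.
- **Access is optional.** It happens on request, so bias is possible rather than certain.
- **No such comparison is planned.** Statistical Approach & Expected Outcomes lists no AE outcome and no AE contrast by product or gender. The DSMB is said only to review the protocol every 6 months for safety.
- **Much is outside the route.** CPD comes from the participant's smartphone diary. Serious and grade 4-5 events do not depend on attribution. The American Thoracic Society questionnaire (ATSQ) collects cough, wheeze, phlegm and breathlessness by self-report at each visit, so it would be wrong to say that filtered respiratory symptoms leave no trace. Source documentation is also required for all AEs.
- **Silence is weak evidence.** The opening of the blinding paragraph is not readable in the available text, and Protection against Risks points to a data and safety monitoring section that is not there either.
- **The definition and the recording rule can coexist.** One says what an AE is, the other which AEs are recorded. This is not a contradiction.

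All of this stands and narrows the point. It does not remove it. The person who oversees attribution can have the code, nothing readable requires attribution to be fixed first, and the recording rule for grades 2-3 depends on it. The notification sentence does not close the gap: it is unclear whether it covers release on request, and it does not move attribution to someone still blinded.

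**Conclusion.** The point holds in a limited form. Knowledge of the product could change which non-serious grade 2-3 AEs are recorded on nicotine versus placebo. It is a weakness in descriptive safety data and no threat to the primary outcome.

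Its size cannot be derived from the documents. With equal true rates and an assumed 60/40 split, the spurious recorded ratio is 1.5 if every attribution is made knowing the code, about 1.1 if a quarter are, and 1.0 if none are. The 1.5 should not be read as an expected value, because it needs both the assumed split and complete unblinding. The conclusion also rests on reading the blank Table 4 cells as merged (for grade 3) and on no condition being stated in the unreadable part of the blinding paragraph. The change is worth making because it costs little.

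**What to change.** In Procedures (Phases 2 & 3) and Measures (respiratory and other symptoms), state that:

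1. grade, attribution and the decision to record or not are entered and time-stamped in the TRTP database before any non-urgent release of the SREC condition for that participant;
2. each release is logged with date and reason;
3. if the code was released first, attribution is made by a physician or delegated medical-team member who has not received it.

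Emergency access stays as it is. An alternative is to record all grade 2-3 AEs and tabulate them by condition whatever their attribution, which cuts the link between attribution and recording. Under either change, the difference due to assessor knowledge in the calculation above becomes zero.

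The first option costs a paragraph, a time stamp and a short data-entry step before a non-urgent release. The alternative costs some additional AE recording.
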